I developed a brief, person-centered PA support program, called *Move*, designed to enhance explicit autonomous motivation for PA in adults with overweight or obesity. The *Move* program is based on the Self-Determination Theory (SDT) and targets enhanced PA adherence. *Move* supports autonomous motivation for PA by encouraging adults in choosing PA types that are personally meaningful and intrinsically motivated. SDT is compelling to focus on in the context of PA because it distinguishes the quantity from the quality of explicit motivation for PA. Autonomous motives, in contrast to controlled motives (e.g. rewards, guilt), are considered high-quality because PA is perceived to be consistent with individual values and inherent interests.³⁵ The quality of explicit motivation is determined by the extent to which a context (e.g. exercise) satisfies 3 basic psychological needs: autonomy (actions are authentic and freely chosen), competence (feeling capable of achieving goals), and relatedness (connection to others).³⁵ My work and the work of others has demonstrated that explicit motivation predicts PA adoption and maintenance.³⁶ I found that adults with autonomous PA motives sustained their initial increases in PA at 12 months whereas those with controlled PA motives did not.³⁷ These data, among others^{11-13, 38}, suggest the importance of autonomous motives for PA adherence and provided key insight for *Move*.

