However, participants were not randomized to receive *Move* and results are likely confounded by other factors, including overall attendance to group-based classes (78% vs. 60%, $p<0.01$). Importantly, qualitative data supports our intervention, as participants ($n=39$) reported high enthusiasm and acceptability for the *Move* program (abstract, *ObesityWeek 2021*). One participant stated: “You begin to enjoy [PA] because it becomes part of you. If you start moving in ways that you actually enjoy, it’s no longer a chore. It’s something that you just do.” Participants also indicated a strong desire for additional *Move* program content.

IV. Research Methods

The study will take place at the University of Colorado Anschutz Medical Campus (CU-AMC). The overall objective is to engage research partners to refine *Move+* (Aim 1, Phase 2). Results will inform a future pilot feasibility trial of the refined *Move+* intervention.

A. Outcome Measure(s): To achieve Aim 1 Phase 2, quantitative and qualitative data will be collected. Human-centered design testing^{47, 48} will occur using a 12-week, single-arm field trial where a Registered Dietitian (RD) delivers ≥ 1 *Move+* session per week (group-class, 1:1, and/or guided imagery), remotely. Patients will receive a 12-week online fitness membership, using the option with the highest acceptability from cycle 1. Research partners recommendations will be used to refine intervention components. See **Table 1** for a description of the assessments by research partner type. The **primary study outcomes** are acceptability and feasibility of the *Move+* intervention. Other pre-specified study outcomes include exploring changes in SDT-constructs, explicit motivation for PA, implicit attitudes towards PA, weight, waist circumference, PA patterns, and cardiovascular markers.

Table 1. Assessments for Aim 1, Phase 2 by Research Partner Type

Outcome	Measure	Description	Participants (n=9)	RD (n=1)	Week 0	Week 12
Acceptability	90-min Semi-structured Focus Group via Zoom*	Explore acceptability; Identify any issues with the Move+ components		x		x
	Semi-structured 60-min Interview ⁴⁹ via Zoom*	Record reactions around acceptability using videoconferencing; identify any issues with the refined Move+ components		x		x
	Net Promoter Score (NPS) ⁵⁰	Scale -100 to 100; scores >0 indicate good acceptability	x	x		x
	Acceptability of Intervention Measures		x	x		x

(AIM) ⁵¹					
Intervention					

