Appropriateness Measure (IAM) ⁵¹		x	x	x	x
Likert scale (0-10)	Ratings of satisfaction for intervention component(s) by patients and staff every 3 weeks	x	x	x	x
Feasibility of Intervention Measure (FIM) ⁵¹		x	x	x	x
Perceived Characteristics of Intervention Scale (PCIS) ⁵²	PCIS measures trialability, relative advantage, compatibility, complexity, potential for intervention adaptation, etc.		x	x	x
Organizational Readiness for Knowledge Translation (OR4KT) ⁵³	Setting-level factors that influence program adoption (organization climate, organization context, change content, leadership, organizational support, motivation)		x	x	x
Reach/Recruitment	# of patients screened, proportion of eligible screens who enroll	x		x	
Treatment Adherence	[# sessions attended/# provided], self-reported fitness membership usage	x		x	
Outcome Measure Rates	[# patients who complete measures at each time point/# patients randomized]	x	x	x	x
Retention	[# patients who complete 12-wk intervention/# patients who start the intervention]	x		x	
Fidelity and Adaptations	Direct Observation	Move+ sessions will be recorded, and the study PI will review recordings using an a-priori checklist		x	x
Physical Activity Patterns	Accelerometer	The activPALv4 (PAL) will be worn over 7 days to capture total stepping time, stepping time in MVPA, and sedentary behavior	x	x	x
	Global Physical Activity Questionnaire (GPAQ)	The GPAQ consists of 16 items which ask about the time spent doing different types of physical activity in a typical week	x	x	x
	Exercise and Sleep Log	Participants will be asked to record exercise and sleep over 15 days	x	x	x
SDT-constructs	Basic Psychological Need Satisfaction and Frustration Scale - Exercise (BPNFS-E) ⁵⁴	SDT-based; Assesses satisfaction vs. frustration with basic psychological needs for autonomy, competence, and relatedness with regards to engaging in physical activity (for participants) or teaching the program (for providers)	x	x	x
Explicit PA Motivation	Behavioral Regulations for Exercise Questionnaire ⁵⁵	SDT-based; Provides separate scores for each behavioral regulation for exercise (amotivation, external, introjected, identified, integrated, and intrinsic)	x	x	x
Implicit Attitudes	Single	A computerized, time sorting	x	x	x

Towards PA	Category Implicit Association Test ⁵⁶	task, which asks participants to rapidly indicate, whether each presented PA stimulus belongs to one of two attributes (good/bad)			

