C.2.1 Description of *Move+* Intervention: The *Move+* components are 1) group-based classes, 2) individual support sessions (for personalized support), 3) guided mental imagery sessions (to address negative feelings around PA), and 4) low-cost, virtual fitness membership (to improve PA access). I worked with Drs. [name] and [name] to develop *Move+* curriculum (see **Table 2**) that targets SDT constructs.⁶⁵ The group-based sessions serve as the core curriculum for *Move+*, and three 1:1 support sessions help participants adopt the 3 PA messages from each group-based class into their daily lives. These 3 PA messages were inspired by a prior publication¹⁴. For the membership to livestream fitness classes, participants will receive 12-weeks, using the option with the highest acceptability from Aim 1 Phase 1 (COMIRB # 22-0147). The guided positive exercise imagery scripts were developed based on work from Williams et al.⁶⁶ and prompt several sensory and emotional experiences.⁴⁵

Table 2. Description of Move+ Intervention Activities, Targeted SDT Constructs, and Organizational-Level Personnel for Intervention Delivery			
Component	Move+ Activities	Targeted SDT Constructs	Organizational Delivery Mechanism
Core Curriculum of Move+ Program			
Group-Based Classes	There will be 1 introduction group-based class, in addition to the 3 group-based sessions. Each of the 3, 60-min group-based sessions will focus on an autonomy-supportive PA message: 1) "All movement counts", 2) "Move in ways that make you feel good", and 3) "By moving more, you take better care of	Autonomy, Relatedness, Competence	Trained* Registered Dietitian (RD) teaches class via Zoom Videoconferencing

yourself". All group-based classes will be digitally recorded for fidelity checks.
 
Additional SDT-based Move+ Components
			
Individualized 1:1 Support Sessions	
 3, 45-min sessions to tailor PA messages & develop clear plan of action for PA Encourage support of friends/family, demonstrate interest in person, use empathetic listening All individualized support sessions will be digitally recorded for fidelity checks. 	Relatedness, Competence	Trained* RD provides via Zoom Videoconferencing

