- **Organizational Readiness for Knowledge Translation (OR4KT) Questionnaire:** At the end of the 12-week field trial, the RD partner will be asked to complete the OR4KT. The OR4KT is a 59-item survey that measures setting-level factors that influence program adoption (organizational climate for change, organizational contextual factors, organizational willingness to adjust to changes, leadership, organizational support, and motivation).⁵³ Subscales are grouped into 6 dimensions: 1) Organizational climate for change (10 items), 2) organizational contextual factors (10 items), 3) Change content (9 items), 4) Leadership (10 items), 5) Organizational support (10 items), and 6) motivation (10 items), followed by 1 open-ended question. The validity and reliability of the OR4KT will be assessed in real-life contexts of implementation of evidence-based changes in healthcare.⁵³ Participant partners will not be asked to complete this scale.
- **Global Physical Activity Questionnaire (GPAQ)**^{69, 70}: At baseline and week 12, patient partners will be asked to complete the GPAQ with showcards. The GPAQ is a 16-item interview-based questionnaire, where a research staff member will ask participants to estimate time spent doing different types of physical activity in a typical week. The research staff member will use showcards to help the participant understand types of activities considered moderate vs. vigorous intensity.
- **Basic Psychological Need Satisfaction and Frustration Scale - Exercise (BPNSFS-E)**⁵⁴: At week 12, patient partners and provider partners will be asked to complete the BPNSFS-E. The BPNSFS-E is a SDT-based questionnaire. It assesses satisfaction vs. frustration with basic psychological needs for autonomy, competence, and relatedness with regards to exercise through 12 items (e.g., “The way I exercise is in agreement with my choices and interests”) and a five-point Likert scale, where 1 = “I don’t agree at all” and 5 = “I completely agree”). This 24-item questionnaire has demonstrated validity⁷¹ and gender invariance.⁷²
- **Behavioral Regulations for Exercise Questionnaire (BREQ-3)**⁵⁵: At baseline and week 12, patient partners will be asked to complete the BREQ-3. The BREQ-3 is SDT-based and provides separate scores for each behavioral regulation for exercise (amotivation, external, introjected, identified, integrated, and intrinsic). There are 24-

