- **Body dissatisfaction**: At baseline and week 12, patient partners will be asked to rate their degree of body dissatisfaction. We will measure this using the Figure Rating Scale (FRS) developed by Stunkard et al⁷⁸. Respondents are asked to choose the image that better represents their actual size. Then, they are asked to choose which image represents their ideal body size. The first is considered a measure of perception of one's body (current body image); the second is understood as an adherence to the ideals of beauty socially shared in the culture to which the respondent belongs (ideal body image). The discrepancy between the two is considered a good measure of body dissatisfaction. Positive scores are indicative of the desire to have a larger body size, while the negative ones are indicative of the desire to be thinner. The FRS has indicated good test-retest reliability and moderate correlations with other measures of body image dissatisfaction, eating disturbance, and overall self-esteem.⁷⁹
- **Identity**: At baseline and week 12, patient partners will be asked to rate their level of agreement for each physical activity identity statement. This will be measured using the Behavior Based Identity Questionnaire, which consists of 4 items.⁸⁰
- **Physical Activity Habit Strength**: At baseline and week 12, patient partners will be asked to rate their level of agreement for each physical activity habit statement. The Self-Report Index of Habit (SRHI) Index Strength involves 12-items that assesses physical activity habit strength and automaticity^{81, 82}.
- **Dietary Intake Assessment**: Dietary energy and fat intake will be assessed with a 3-day dietary record. Participants will be asked to log food intake over 3 days including a weekend day.
- **Environment**: Participants will be asked to report their home address, work address, and any changes in these addresses over the 12-week intervention. Home address and work address will be used to obtain census level data about the area in which they live and work, like access to parks and grocery stores.

- **Medication Review:** We will ask patient partners about the medications they are taking at baseline and week 12.

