Making correct inferences when coding qualitative data: There is a risk of making incorrect inferences when coding the qualitative data. However, we will use an iterative process that involves moving back and forth between raw data and emerging themes multiple times, to ensure that participants' experiences are accurately captured. We use a team-based approach to code the qualitative data.

Compliance with *Move+* Intervention: We recognize adherence to PA will not be perfect and we do not expect it to be. The research question we seek to address is not whether participants will fully adhere to the *Move+* program, but rather whether the *Move+* program components are acceptable and feasible.

F. Data Analysis Plan:

F.1 Quantitative Data Analyses: Descriptive statistics will be performed on scale ratings with aspects of the *Move+* program. Aspects of the *Move+* program with less acceptable ratings will be targeted for refinement. Average scores <0 for the Net Promoter Score®, or <3 on any scale from the PCIS will indicate areas for refinement. Demographic information will be analyzed using descriptive statistics. We will also explore within-person changes in other pre-specified outcome measures from baseline to 12 weeks (e.g., PA, weight, waist circumference, blood pressure, cardiovascular fitness) using a paired samples t-test. Normality assumptions will be evaluated, and transformations used (e.g., square root and log) as appropriate. P-values <0.05 will be considered significant. No interim analysis is planned.

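### The BPNSFS-E is scheduled at week 12 with no baseline, so the pre-specified change in SDT-constructs cannot be computed if that sentence is followed

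*Combined protocol and SAP*

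**What the plan says.** Section D, Outcome Questionnaires, gives the timing of the BPNSFS-E in one sentence: "At week 12, patient partners and provider partners will be asked to complete the BPNSFS-E". No earlier administration is mentioned.

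Section IV.A frames the outcome as a change: "Other pre-specified study outcomes include exploring changes in SDT-constructs, explicit motivation for PA". The justification paragraph that closes the questionnaire list repeats that changes in SDT-based constructs are among the other pre-specified outcomes.

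Table 1 has one row for SDT-constructs, and its only measure is the BPNSFS-E, described as follows: "Assesses satisfaction vs. frustration with basic psychological needs for autonomy, competence, and relatedness".

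Section F.1 says the study will explore "within-person changes in other pre-specified outcome measures from baseline to 12 weeks" with a paired samples t-test. The outcomes it lists in brackets are examples and do not include SDT-constructs. However, the sentence covers the other pre-specified outcomes as a class, and section IV.A puts SDT-constructs first in that class.

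**The concern.** A within-person change needs two measurements per person, and the questionnaire text schedules one. If staff work from that text, the study reaches week 12 with no starting value on the only scale assigned to this outcome. The loss is permanent, because a pre-intervention score cannot be obtained once the programme has begun.

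The construct is central to the rationale. Section II presents autonomy, competence and relatedness as the three needs that determine the quality of motivation. Table 2 in section C.2.1 names one or more of them as the target of every *Move+* component. Without a baseline, the pilot cannot describe whether these needs moved at all.

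**Working it through.** The plan gives no effect size, SD or power for this outcome, so there is no figure of its own to reproduce. The check compares the passages and counts.

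**1. Is week-12-only timing the norm for such measures?** The entries in section D, Outcome Questionnaires, from the GPAQ to the medication review describe these participant measures:

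| Timing in the text | Measures | Count |
|---|---|---|
| Baseline and week 12 | GPAQ, BREQ-3, SC-IAT, VMIA-2, MIQ-3, WBIS-M, Figure Rating Scale, identity, habit strength, medication review | 10 |
| No visit named | 3-day diet record, environment | 2 |
| Week 12 without baseline | BPNSFS-E | 1 |

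10 + 2 + 1 = 13. The BPNSFS-E is the single exception. The earlier entries placed at the end of the trial (AIM, IAM, FIM, NPS, PCIS, OR4KT) serve acceptability, feasibility and implementation, and are not change outcomes. The plan gives no reason for collecting the BPNSFS-E only at the end.

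**2. Can the planned analysis be run?**

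- Assessments needed per person for a paired t-test: 2.
- Assessments named for the BPNSFS-E: 1.
- Participant partners (section B.1): 9.
- Change scores as written: 0 of 9. With a baseline added: up to 9 of 9.

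**3. Does another measure fill the gap?** The nearest is the BREQ-3, which has both visits. It "provides separate scores for each behavioral regulation for exercise (amotivation, external, introjected, identified, integrated, and intrinsic". These are six regulations, and none is one of the three needs. Table 1 also files it under a different outcome, explicit PA motivation. Table 2 assigns need targets as follows: group classes 3, individual sessions 2, online fitness 2, guided imagery 2, a total of 9. All 9 are drawn from autonomy, competence and relatedness, which are what the BPNSFS-E measures.

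**4. Does Table 1 settle the matter?** In the text copy, the BPNSFS-E row shows three marks across four columns (Participants, RD, Week 0, Week 12), and their positions cannot be recovered. The plausible readings are:

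- *Participants, RD, Week 12:* the table repeats the text, and no baseline is scheduled anywhere.
- *Participants, Week 0, Week 12:* the table contradicts the text on timing and on whether the provider completes the scale.
- *All four columns marked in the original:* the text still omits the baseline.

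The sentence needs correcting under each of them.

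**5. What would a baseline buy?** For n pairs, the half-width of the 95% confidence interval, in SDs of the change, is t(0.975, n−1)/√n. For n = 9 this is 2.306/3 = 0.77. A two-sided 5% paired t-test (two-sided is assumed; the plan does not say) has 80% power at the standardised change d for which a noncentral t with n−1 degrees of freedom and noncentrality d√n exceeds the critical value with probability 0.80.

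| Pairs (7 and 8 are assumed completer numbers) | CI half-width (SD of change) | d at 80% power |
|---|---|---|
| 9 | 0.77 | 1.07 |
| 8 | 0.84 | 1.16 |
| 7 | 0.92 | 1.27 |

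The single provider allows at most a descriptive difference.

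**The case against.** The best counter-argument is that Table 1 probably already schedules a baseline. In the text copy, the BPNSFS-E row has the same run of marks as the GPAQ and BREQ-3 rows, which the text places at baseline and week 12. The NPS and AIM rows, completed by participants and the RD at week 12, look different. A team working from the table would then collect the baseline, and the defect would be one sentence out of step with its table. This has some force and is why the loss is stated conditionally. It is not decisive. Alignment elsewhere in the table is visibly unreliable: the IAM and FIM rows show four marks although the text places both at the end of the trial. The BPNSFS-E row also describes a provider version. Even on this reading, the text and the table conflict and must be reconciled.

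A second argument is that the outcome is exploratory and that nine pairs give an imprecise estimate. Both points are true, and they limit how serious this is. They do not justify a schedule under which a pre-specified change has no data.

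A third is that the same entry describes the scale as having both 12 items and 24 items, and that Table 1 gives providers a different referent (teaching the programme). Both observations are correct. They are separate matters to settle when the entry is edited, and they do not affect the point about timing.

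**Conclusion.** The concern holds. As written, the questionnaire text provides one assessment where the planned analysis needs two, so 0 of up to 9 participants would have a change score for SDT-constructs. With a baseline, up to 9 would. The count is conditional on staff following that sentence; if the original Table 1 marks Week 0 and staff follow the table, the baseline may be collected despite the text.

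One exploratory outcome is affected. The primary acceptability and feasibility outcomes, and the F.1 refinement thresholds on the NPS and PCIS, do not depend on this scale. It should still be fixed, because the loss could not be recovered and the repair costs almost nothing.

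**What to change.** Reword the timing sentence in the BPNSFS-E entry so that patient partners complete the scale at baseline and again at week 12, and the provider partner at week 12, as the text now has it. Then check that the SDT-constructs row of Table 1 agrees on who completes the scale and at which visits. While the entry is open, state which item count applies and whether the provider answers about exercise or about teaching, so that both administrations use the same form.

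The cost is one edited sentence, a check of one table row, and one more questionnaire at a baseline that already includes nine other questionnaires or tests. Sample size, analysis method and primary outcomes do not change.
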